4.3 Final Analysis

After all comments on the pre-final analysis have been resolved and the study database is declared final, the final analysis will be generated. Final tables, figures, and listings (TFLs) will be provided approximately 1 week after the study database is declared final. This includes the full set of Part A TFLs and Part B TFLs. If there were no changes to the pre-final analysis or the study database, the pre-final TFLs may be considered final.

5 CHANGES FROM PROTOCOL-SPECIFIED STATISTICAL ANALYSES

For Part B analysis of LFC as measured by MRI-PDFF, the ANCOVA model specified in the Protocol includes both baseline LFC as a covariate and LFC stratification (3 categories) as a factor. Since this is redundant information, LFC stratification as a factor will be dropped as a covariate from the model; baseline LFC as a covariate is sufficient.

After Part A analysis was completed, the Per-Protocol Population definition was updated to require subjects to finish the 12-week Treatment Period. However, this part of the definition is excluded for analysis. Instead, the Part B Per-Protocol Population is clarified to require $\geq 60\%$ study drug compliance.

There are some other minor changes from the protocol-specified statistical analyses detailed in this SAP:

- Week 12 included for biomarkers of liver fibrosis and inflammation, as appropriate;
- Study endpoints and definition of mITT Population updated to clearly allow patients with ET assessments (not just Week 12 assessments) to be included.
- HbA1c is not analyzed at Week 2 and Week 12 with the other lipid and metabolic profile parameters.

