6.3.3.7 Day 84 (Week 12)

The following procedures will be performed at Day 84 (Week 12):

- Record changes in concomitant medications.
- Perform brief physical examination.
- Measure body weight and calculate BMI.
- Measure waist and hip circumferences.
- Calculate WHR and WHtR.

- Collect vital signs (systolic and diastolic blood pressure, heart rate, respiratory rate, and body temperature) with the patient in the sitting position after 5 minutes of rest and before any blood draws.
- Administer the AUDIT-C test.
- Counsel on diet/lifestyle.
- Collect blood sample for the following:
 - Chemistry, hematology, coagulation, and lipid and metabolic profile.
 - Sparse PD (predose [fasting]).
 - Sparse PK (predose [fasting]).
 - Plasma storage.
- Collect urine sample for urinalysis and pregnancy test. If the pregnancy test is positive, perform serum hCG test.
- Perform 12-lead ECG.
- Perform MRI-PDFF and cT1 imaging.
- Perform FibroScan VCTE (optional).
- Assess adverse events.
- Collect returned used/unused study drug and assess compliance.

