7.1.2 Secondary Efficacy Variables

The secondary efficacy variables include the following:

- Proportion of patients with $\geq 5\%$ absolute reduction in LFC as measured by MRI-PDFF from baseline to Week 12
- Proportion of patients with $\geq 10\%$ absolute reduction in LFC as measured by MRI-PDFF at Week 12
- Proportion of patients with $\geq 20\%$ absolute reduction in LFC as measured by MRI-PDFF at Week 12
- Proportion of patients with a relative reduction in LFC $\geq 20\%$ as measured by MRI-PDFF at Week 12
- Proportion of patients with a relative reduction in LFC $\geq 30\%$ as measured by MRI-PDFF at Week 12
- Percent change (relative reduction) in LFC as measured by MRI-PDFF from baseline to Week 12
- Change and percent change in imaging-derived mean cT1 from baseline to Week 12
- Change and percent change in WHR from baseline to Week 12 (Part B only)
- Change and percent change in WHtR from baseline to Week 12 (Part B only)
- Change in the following biomarkers of liver fibrosis and inflammation: ALT, AST, AST/ALT ratio, adiponectin, high sensitivity C-reactive protein, interleukin 6, tumor necrosis factor alpha, cytokeratin-18, fibronectin, hyaluronic acid, procollagen type III N-terminal peptide, tissue inhibitor of metalloproteinases-1 (and derived enhanced liver fibrosis score), Pro-C3, and chitinase-3-like protein 1 (also known as YKL-40) from baseline to Week 4, Week 8, and Week 14/ET, as applicable

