- s. Single 12-lead ECGs will be performed at screening; on Days 14, 28, 56, and 84; and at the EOS and ET Visits after the patient has been resting in the supine position for at least 10 minutes. In case of evident bad quality of the tracing (eg, muscle tremor), the ECG will be repeated. QT interval corrected for heart rate using Fridericia's formula will be measured.
- t. FibroScan with the use of a probe appropriate for the patient's stature for VCTE assessment of LSM for fibrosis and CAP for steatosis with cut-off values LSM ≥ 8.5 kPa and CAP > 300 dB/m, respectively. Patients do not need to undergo a CAP assessment if their medical records indicate an MRI-PDFF LFC $\geq 10\%$ within the 12 months prior to screening. Assessments at Day 84 and ET Visits are optional.
- u. Perform if FibroScan values (LSM and CAP) are within eligibility range; MRI-PDFF using standardized imaging acquisition calibration protocol and central reading to be performed at screening (as baseline value) and Week 12 or ET.
- v. Perform only for patients on study drug for ≥ 4 weeks.
- w. Diet/lifestyle counseling will occur as per standard of care at screening and on Days 1, 14, 28, 56, and 84; and at the EOS and ET Visits. High-level dietary and physical activity guidelines will be provided and documented in the eCRF.
- x. Sparse PD sampling will occur predose (fasting) at the following visits: Days 1, 14, 28, 56, and 84. A sample will also be collected at the EOS and ET Visits. Pharmacodynamic sampling will assess plasma levels of C4; FGF19; and total, primary, and secondary bile acids (such as CDCA, DCA, LCA, and/or others as appropriate).
- y. At the ET Visit (if applicable), a PK/PD sample should be collected, preferably within 24 to 48 hours of last intake of study drug. The date and time of the PK/PD draw and the last dose of study drug must be recorded in the eCRF.
- z. Liver fibrosis and inflammation parameters include ALT, AST, AST/ALT ratio, adiponectin, high sensitivity C-reactive protein, interleukin 6, tumor necrosis factor alpha, cytokeratin-18, fibronectin, hyaluronic acid, procollagen type III N-terminal peptide, tissue inhibitor of metalloproteinases-1 (and derived enhanced liver fibrosis score), Pro-C3, and chitinase-3-like protein 1 (also known as YKL-40).
 - aa. Sparse PK sampling will occur predose (fasting) at the following visits: Days 1, 14, 28, 56, and 84. A sample will also be collected at the EOS and ET Visits.

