APPENDIX B: CLINICAL LABORATORY ANALYTES

Serum Chemistry Panel

Alanine aminotransferase (ALT)	Gamma-glutamyl transferase
Albumin	Glucose
Alkaline phosphatase	Lactate dehydrogenase
Amylase	Potassium
Aspartate aminotransferase (AST)	Sodium
Blood urea nitrogen	Total bilirubin [1]
Calcium	Total protein
Creatine kinase (CK)	Uric acid
Creatinine	
CK-muscle/brain	
Estimation of glomerular filtration rate by the Modification of Diet in Renal Disease formula	
1. If >upper limit of normal, add conjugated (direct) bilirubin.	

Additional Chemistry Parameters

Alpha 2 macroglobulin	Ferritin
Autotoxin	Phosphate
Cardiac troponin I	

Efficacy Parameters

ALT	Adiponectin
AST	Cytokeratin-18
AST/ALT ratio	Interleukin 6
Iron-corrected T1	Fibronectin
High sensitivity C-reactive protein	Procollagen type III N-terminal peptide
Tumor necrosis factor alpha	Pro-C3
Chitinase-3-like protein 1 (also known as YKL-40)	Tissue inhibitor of metalloproteinases-1 (and derived enhanced liver fibrosis score)
Hyaluronic acid	

Pharmacodynamic Parameters

7 α hydroxy-4-cholesten-3-one	Fibroblast growth factor 19
Total bile acids	Chenodeoxycholic acid [1]
Deoxycholic acid [1]	Lithocholic acid [1]
1. Plasma levels of total, primary, and secondary bile acids may be assessed as appropriate.	

Lipid and Metabolic Profile

Branched-chain amino acid concentrations [1]

Hemoglobin A1c

Homeostatic model assessment for insulin resistance (morning fasting glucose and insulin)

Lipoprotein insulin resistance index by nuclear magnetic resonance based on serum cholesterol, high-density lipoprotein cholesterol, low-density lipoprotein (LDL) cholesterol, triglycerides, apolipoprotein B, small dense-LDL, and lipoprotein(a)

Lipoprotein particle size

Small LDL particle number

Small very low-density lipoprotein (VLDL) particle number

VLDL size

1. Liver function test.

Endocrinology

Human chorionic gonadotropin (hCG) [1]

Free triiodothyronine

Thyroid-stimulating hormone

Follicle-stimulating hormone (FSH) [2]

Free thyroxine

1. Serum hCG pregnancy test at screening and at study exit (whether at the End of Study or Early Termination Visit). Only urine hCG tests will be performed at all other study visits. If the urine hCG test is positive, pregnancy will be confirmed by a serum hCG test.
2. FSH level will be measured at screening to confirm postmenopausal state in women ≤55 years of age.

Coagulation

Activated partial thromboplastin time

Fibrinogen

International normalized ratio

Prothrombin time

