3.1.4 Analysis Visits

Refer to SAP V1.0 for Part A analysis visits.

Part B

For LFC, cT1, LSM and CAP, analysis visits will be assigned according to the labelled visit. I.e. "Baseline" analysis visit will be sourced from the "Screening" visit, and "Week 12/ET" analysis visit will be sourced from the "Week 12" or "ET" visit. Note that the ET assessment will be performed only for patients on study drug for ≥4 weeks.

For all other efficacy assessments with regular scheduled visits, analysis visits will be assigned according to the labelled visit. In addition to maximize the data available for assessments with regular scheduled visits, where possible, results from ET and unscheduled visits will be allocated to a post-baseline scheduled visit according to the following rules and visit windows

described in the table below (defined as the halfway point between the target visit days). If a valid value exists for the scheduled visit to which the ET/unscheduled visit has been allocated then the value from the scheduled visit will be used in the analysis, otherwise the values from the ET/unscheduled visits will be used in the analysis for the particular scheduled visit. If there is more than one assessment within a visit window, then the analysis visit will be assigned by the following priorities:

1. Use the assessment from the visit with the matching visit label.
2. Use the visit closest to the target visit day; in the case of ties, use the earlier visit.

Analysis Visit and Target Analysis Day	Visit Windows (Analysis Days)		
	Group I	Group II	Group III
Baseline	See Section 3.1.3		
Day 14 (Week 2)	2 – 21	2 – 21	
Day 28 (Week 4)	22 – 35	22 – 42	2 – 42
Day 42 (Week 6)	36 – 49		
Day 56 (Week 8)	50 – 61	43 – 70	43 – 77
Day 70 (Week 10)	62 – 77		
Day 84 (Week 12)	78 – 91	71 – 91	
Day 98 (Week 14) EOS FUP	92+	92+	92+
Group I: ALT, AST, AST/ALT Ratio, ALP, Total Bilirubin, Gamma-glutamyltransferase (GGT)			
Group II: hs-CRP, CK, BMI, Waist Circumference, Body Weight, Waist to Height Ratio, Waist to Hip Ratio, and lipids and metabolic profile			
Group III: HbA1c and all other biomarkers of liver fibrosis and inflammation			

Note that parameters that are considered both efficacy and safety (ALT, AST, CK) will use analysis visit windowing for both the efficacy and safety summaries and analyses for Part A and Part B.

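### The SAP's Part B visit windows for HbA1c and hs-CRP do not match the scheduled draws: the scheduled Week 12 HbA1c is left out of the windowed analysis, and hs-CRP has Week 2 and Week 12 visits with no scheduled sample

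*SAP*

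**What the plan says.** **HbA1c.** Protocol Appendix B lists "Hemoglobin A1c" in the Lipid and Metabolic Profile, with no restriction by visit. Part B draws that profile at screening, on Days 1, 14, 28, 56, 84 and 98, and at ET (Protocol 6.2, 6.3.3, 6.4, 6.5). The Day 84 blood list, for example, includes "Chemistry, hematology, coagulation, and lipid and metabolic profile". SAP 2.1.2 names HbA1c as an endpoint of the lipid and metabolic objective.

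**hs-CRP.** A footnote to the Part B schedule in Protocol Appendix A states: "Liver fibrosis and inflammation parameters include ALT, AST, AST/ALT ratio, adiponectin, high sensitivity C-reactive protein". Part B draws that panel on Days 1, 28, 56 and 98 and at ET. It is not in the Day 14 or Day 84 lists, and Appendix B does not put hs-CRP in the chemistry or metabolic panels. Protocol 7.1.2 sets the change in these markers "from baseline to Week 4, Week 8, and Week 14/ET, as applicable", and SAP 2.1.2 uses the same timepoints.

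**SAP 3.1.4 windows for Part B.** The two groups are defined as "Group II: hs-CRP, CK, BMI, Waist Circumference, Body Weight, Waist to Height Ratio, Waist to Hip Ratio, and lipids and metabolic profile" and "Group III: HbA1c and all other biomarkers of liver fibrosis and inflammation". Group II has analysis visits at Weeks 2, 4, 8, 12 and 14. Group III has them at Weeks 4, 8 and 14 only. If a scheduled visit has no valid value, "otherwise the values from the ET/unscheduled visits will be used in the analysis for the particular scheduled visit".

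**SAP 5.** Among the minor changes from the protocol: "HbA1c is not analyzed at Week 2 and Week 12 with the other lipid and metabolic profile parameters". No reason is given.

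**SAP 3.7.3.** The lipid and metabolic profile is described as collected in Part B on Days 14 and 84 among other days, with descriptive statistics promised for every post-baseline visit.

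**The concern.** HbA1c is a named endpoint, and its end-of-treatment value is the one a reader would expect to see by arm. Under SAP 3.1.4 and 5 the windowed analysis has no such value. The nearest are Week 8, four weeks before treatment ends, and Week 14, two weeks after it ends.

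For hs-CRP the problem runs the other way. The SAP creates analysis visits at which the protocol schedules no sample. Any figure reported there would come from patients who stopped early or had an extra draw, and they do not represent the randomized arms. SAP 5 declares the HbA1c exclusion but does not mention that hs-CRP has no scheduled draw at Weeks 2 and 12.

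**Working it through.** Neither document gives a figure to reproduce here. The check sets scheduled draws against analysis visits.

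**Step 1. Schedule against analysis visits (Part B, post-baseline).**

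| Analyte | Scheduled draws (Protocol 6.3.3, 6.4) | Analysis visits (SAP 3.1.4) | Mismatch |
|---|---|---|---|
| HbA1c | Days 14, 28, 56, 84, 98 | Weeks 4, 8, 14 (Group III) | Weeks 2 and 12 scheduled, not analysed |
| hs-CRP | Days 28, 56, 98 | Weeks 2, 4, 8, 12, 14 (Group II) | Weeks 2 and 12 analysed, not scheduled |

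Both are also scheduled at ET. Days 42 and 70 add liver tests only.

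**Step 2. Where a Day 84 HbA1c goes.** Scheduled samples are assigned by visit label, and Group III has no Week 12 visit. Assignment by date gives the same answer. Part B visits may vary by 3 days, so Day 84 covers days 81 to 87. The Group III windows are days 2–42, 43–77 and 92 onward, which leaves days 78–91 unassigned, and 81–87 lies wholly inside that gap. An ET HbA1c drawn on days 78–91 also has no visit. The last windowed on-drug value is Day 56, which is 84 − 56 = 28 days before the end of treatment. The next is Day 98, which is 98 − 84 = 14 days after it.

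**Step 3. Where scheduled hs-CRP draws go.** With 3 days either way, Day 28 covers days 25–31, inside the Group II Week 4 window (22–42). Day 56 covers 53–59, inside Week 8 (43–70). Day 98 covers 95–101, inside Week 14 (92 onward). None reaches Week 2 (2–21) or Week 12 (71–91).

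**Step 4. How many ET values could fill those windows.** This is an illustration. It assumes that dropout is uniform over days 1–84 and that every dropout attends the ET visit.

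- Planned dropout of 13% (protocol and SAP): 90 × 0.13 = 11.7 patients. Week 12 window, days 71–84: 11.7 × 14/84 = 1.95, or 0.65 per arm. Week 2 window, days 2–21: 11.7 × 20/84 = 2.8.
- Assumed dropout of 25%: 90 × 0.25 = 22.5 patients. Week 12: 22.5 × 14/84 = 3.75, or 1.25 per arm. Week 2: 22.5 × 20/84 = 5.4.

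Unscheduled draws would add to these, by a number the documents do not give.

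**Step 5. The SAP against itself.** SAP 2.1.2 classes both analytes as the protocol does. SAP 3.7.3 has the metabolic profile collected on Days 14 and 84 and summarised at each visit, while Section 5 leaves HbA1c out at both. The conflict therefore does not depend on how the protocol is read.

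**Step 6. After a swap.** HbA1c in Group II would have a scheduled draw behind Weeks 2, 4, 8, 12 and 14. hs-CRP in Group III would have one behind Weeks 4, 8 and 14. No analysis visit would lack a scheduled sample.

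**The case against.** The strongest reply is that the SAP may be right about what was measured. The documents give the schedule, but the Laboratory Manual is not among them, and nothing shows which analytes were run at which visit. SAP version 4.0 is dated July 2021, after the Part B interim analysis of February 2021, so its grouping could reflect the data in hand. Its window table and its Section 5 line on HbA1c agree with each other. This stands, and it sets the order of the fix: regrouping before checking could remove real hs-CRP data and create empty HbA1c visits. It does not remove the mismatch, because SAP 2.1.2 and 3.7.3 would then be wrong as well as the protocol.

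A reader might infer more than the documents support:

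- **That collected Week 12 HbA1c data are thrown away.** Collection is not shown. Any values would still be listed under SAP 6, and SAP 3.7.3 read alone would summarise them.
- **That an HbA1c hypothesis test is lost.** The repeated-measures model in SAP 3.4.2.5 covers lipoprotein profiling parameters. HbA1c is not named there or in any other model, and it is not among the efficacy variables in Protocol 7.1.2.
- **That the SAP commits to testing hs-CRP at Weeks 2 and 12.** SAP 3.4.2.1 specifies a Wilcoxon analysis with a Hodges-Lehmann estimate but names no visit, and it refers to available markers and to visits as appropriate. The windows permit such a comparison; the text does not clearly require it. The Section 5 line adding Week 12 for fibrosis markers makes sense for ALT and AST, which have a Day 84 chemistry draw.
- **That Week 12 should be the main HbA1c timepoint.** Neither document names a main timepoint, and none needs to be added.

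**Conclusion.** The mismatch is real. For Part B, SAP 3.1.4 groups HbA1c and hs-CRP the opposite way to the protocol's schedule and to SAP 2.1.2 and 3.7.3. If collection followed the protocol, the scheduled end-of-treatment HbA1c is left out of the windowed analysis. That would concern about 26 planned completers per arm, a planning figure. hs-CRP would have two analysis visits with no scheduled draw, filled by about 2 ET values in 90 patients at Week 12 and about 3 at Week 2 under the Step 4 assumptions at 13% dropout.

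The classification and schedule conflict is certain from the text. The effect on the data is conditional on what the laboratory ran. Only secondary laboratory markers are involved, and the primary liver-fat analysis is unaffected. Part A windows are in SAP V1.0, which is not available here, so nothing is concluded for Part A. The point is worth correcting because the correction is nearly free, but it does not threaten the trial's main conclusion.

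**What to change.** 1. Confirm from the laboratory data at which Part B visits HbA1c and hs-CRP were run. Decide for each analyte separately.
2. If collection followed the protocol, move HbA1c to Group II in SAP 3.1.4 and delete the HbA1c line in SAP 5, so that Week 12 is summarised and SAP 5 no longer conflicts with 3.7.3. Move hs-CRP to Group III, so that no Week 2 or Week 12 comparison is made. ET hs-CRP draws on days 78–91 would then have no visit, as already holds for the other Group III markers; the SAP should say whether that is intended.
3. If collection followed the SAP grouping, correct the protocol schedule and SAP 2.1.2 and 3.7.3 to match, and state the reason in SAP 5.

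The cost is one check of the laboratory data, a few lines of SAP or protocol wording, and a change of window group for two analytes in the programming. No new samples are needed.

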6 PROGRAMMING SPECIFICATIONS

Analyses will be performed using SAS[®] version 9.4 or higher. All available data will be presented in patient data listings which will be sorted by patients and visit date as applicable. Detailed Programming Specifications will be provided in a separate document(s).
